9. RISKS

a. **Potential Risks**

i. Investigational devices

NA

ii. Investigational drugs

[name] has applied USPIO ultra small superparamagnetic iron oxides as MR contrast agents in phase II and III clinical trials in adult patients. In addition, [name] has currently two active clinical trials on the use of ferumoxytol in children for MR imaging of bone lesions and for whole body tumor staging. The USPIO contrast agents

are very well tolerated and show excellent safety profiles. The delivered iron dose via a typical ferumoxytol administration is in the order of 150-500 mg iron oxides note that these are coated iron particles, not free iron, which is equivalent to or lower than the iron dose administered with one blood transfusion. USPIO are slowly metabolized in the liver and not excreted via the kidneys. Thus, they are safe to use in patients with renal insufficiencies and are not associated with any risk of nephrogenic sclerosis a potential adverse event after injections of certain gadolinium chelates. Expected risks include dizziness and nausea, possible localized twitching sensation, etc. Anaphylaxis or anaphylactoid reactions were reported in 0.2 of subjects, which is in the order of other MR contrast agents.

iii. Commercially available drugs, biologics, reagents or chemicals

NA

iv. Procedures

MRI w/ contrast Magnetic fields do not cause harmful effects at the levels used in the MRI machine. However, the MRI scanner uses a very strong magnet that will attract some metals and affect some electronic devices. In some cases, having those devices means the participant should be excluded. Additionally, when contrast is injected, as with any intravenous injection, there are risks of bruising, bleeding, or infection from the venipuncture; and allergic reaction to the injected contrast.

v. Radioisotopes/radiation-producing machines

NA

vi. Physical well-being

NA

vii. Psychological well-being

Some small risk of a patient experiencing claustrophobia. This is an infrequent but regular occurrence in any MRI facility. Every effort is made to minimize this risk and the research and clinical staff are well trained to act appropriately.

viii. Economic well-being

NA

ix. Social well-being

NA

x. Overall evaluation of risk

Low - innocuous procedures such as phlebotomy, urine or stool collection, no therapeutic

agent, or safe therapeutic agent such as the use of an FDA approved drug or device.

b. International Research Risk Procedures

NA

c. Procedures to Minimize Risk

An MRI screening form will be completed prior to participation. Any potential contraindication to MRI revealed by the comprehensive screening form will result in participant exclusion. The research team will use the clinical systems and the RedCap database for data management. RedCap is maintained by Clinical Informatics at Stanford University as a HIPAA compliant, secure, encrypted database for research purposes. Data exported by the researchers from these secure systems will only be exported in a deidentified form to minimize risks to confidentiality.

d. Study Conclusion

Endpoint: To generate a non-invasive, easily applicable and widely available MR imaging test for evaluation of kidney transplant rejection. Primary endpoint is to develop a sensitive and reliable, non-invasive and quantitative imaging test for detection of macrophages in kidney transplants as a biomarker for rejection. As a secondary endpoint, since different oxygenation states of iron have scaled but measurable changes on the inherent tissue magnetic susceptibility, we plan to also evaluate the utility of simultaneously generated 3D maps of arterial and venous supplies of kidney transplants, provided by our imaging method, in comparison with ultrasound as the current diagnostic standard. The ultimate goal is to provide a comprehensive evaluation of the morphology, vascular supply and host immune responses in kidney transplants with one single, non-invasive and comprehensive diagnostic test.

In terms of individual participation, each patient's experimental participation is over when their individual MRI is collected, analyzed, and reported. If a patient experiences an anaphylactoid reaction to the study agent during initial administration, participation would be terminated - administration of the agent would be discontinued, counteracting medication would be given, and the patient would not undergo MRI. Such reactions are very rare reported in 0.2 of subjects but anticipated, and as such, the contrast agent is only administered in a clinical setting under the direct supervision of an experienced MD, with access to a crash cart and appropriate anti-anaphylactoid medication.

e. Data Safety Monitoring Plan (DSMC)

- i. Data and/or events subject to review

Of note, [name] has applied iron oxide nanoparticles as MR contrast agents in phase II and III clinical trials in adult patients. These contrast agents are very well tolerated and show excellent safety profiles. The delivered iron dose via a typical

ferumoxytol administration is in the order of 150-500 mg iron oxides note that these are coated iron particles, not free iron, which is equivalent to or lower than the iron dose administered with one blood transfusion. Iron oxide nanoparticles are slowly metabolized in the liver and not excreted via the kidneys. Thus, they are safe to use in patients with renal insufficiencies and are not associated with any risk of nephrogenic sclerosis a potential adverse event after injections of certain gadolinium chelates. Anaphylaxis or anaphylactoid reactions were reported in 0.2 of subjects, which is in the order of or lower compared to other MR contrast agents see FDA report: Lu M, Cohen MH, Rieves D, Pazdur R. FDA report: Ferumoxytol for intravenous iron therapy in adult patients with chronic kidney disease. Am J Hematol. 2010;85 5 :315-9. In the unlikely event of an anaphylactoid reaction, appropriate actions will be taken as with any other contrast agent reaction and the event will be reported to the IRB.

- ii. Person(s) responsible for Data and Safety Monitoring

[name] will serve as the ME. In an unanticipated and unlikely event of any adverse event or anaphylactoid reaction to this contrast agent, appropriate actions will be taken to treat the reaction and the event will be reported to the IRB.

- iii. Frequency of DSMB meetings
NA
- iv. Specific triggers or stopping rules

Any signs of an anaphylactoid reaction, such as rash, urticaria, nausea, cough, breathing difficulty will lead to discontinuation of contrast administration and symptomatic treatment.

- v. DSMB Reporting

The ME will forward written reports to the appropriate entities via email

- vi. Will the Protocol Director be the only monitoring entity? (Y/N)
y
- vii. Will a board, committee, or safety monitor be responsible for study monitoring? (Y/N)
y

f. Risks to Special Populations

The study involves a non-invasive imaging study and the off-label use of an FDA approved drug, with an FDA IND to do so. Side effects for this drug have been observed in less than 0.2 of the population. Informed Consent and Assent are acquired appropriately and all data and safety precautions are observed. Risks are thus assessed as minimal.

10. BENEFITS

Participants may immediately benefit from more accurate assessment of arterial and venous supply to their allograft. In the long term, validating a method for accurately assessing rejection status/health of an allograft without general anesthesia or invasive biopsy reduces risk and cost to the patient.

11. PRIVACY AND CONFIDENTIALITY

All participant information and specimens are handled in compliance with the Health Insurance Portability and Accountability Act (HIPAA) and privacy policies of Stanford University, Stanford Health Care, and Stanford Children's Health.

Non-invasive MR Imaging Diagnosis of Transplant Rejection

NCT02006108

April 6, 2018

Statistical Analysis Plan

[name], PhD, Principal Investigator
Stanford University
Stanford, California 94305

Statistical Analysis Plan

Histopathology

Patients with allografts underwent routine biopsies either on the same day as the MRI, before the MRI, or after the MRI. The biopsy specimens were dissected parasagittally, kept in formalin overnight, dehydrated through graded alcohol washes (70, 95, and 100 %), embedded in paraffin and sliced on a microtome. Five-micrometer thick tissue slices on glass slides were stained with hematoxylin and eosin (HE) and Periodic acid-Schiff (PAS) stains. In addition, the samples were stained with antisera against CD163 (Novocastra, Clone 10D6, 1:50 dilution, performed on the Ventana XT using HIER solution CC1, pH 8.0). The histological and immunohistochemical analysis was performed under a light microscope (Olympus BX51). The biopsy samples were evaluated for cellular and antibody-mediated rejection as per the Banff 2013 criteria. Evidence for other disease processes affecting the allograft was also sought. The CD163 stained slides were scored blinded as follows: no stained cells = 0, G10 positive cells/hpf present in G25 % of biopsy = 1, 910 positive cells/hpf in 26–50 % of biopsy = 2, and 910 positive cells in 950 % of biopsy = 3.

Data Analysis

GFR and MRI data were compared between patients with non-rejecting and rejecting allografts using the two-sided t test. In addition, mean T2* values of whole kidneys as well as kidney cortex and medulla were compared between the three patient groups of native, non-rejecting and rejecting allografts using analysis of variance (ANOVA). In addition, T2* relaxation times were correlated with the CD163 score, using a linear regression analysis. All statistical computations were performed with Microsoft Excel software. An alpha level of 0.05 was chosen to indicate significant differences.

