2. STUDY PROCEDURES

a. Procedures

The patients and their parents will be informed about the nature of the study and a written informed consent will be obtained. 12-24 h before a planned MRI study, Ferumoxytol will be administered intravenously at a dose of 5 mg Fe/kg over approximately 1-2 minutes. The blood pressure and respiratory rate will be monitored before and directly after the injection, and the patients will be observed for any potential adverse events for at least 30 minutes after the iron oxide administration. The patients will undergo MR imaging at 1-7 days after iron oxide injection. For some patients, we have the option to get a MR- exam before the injection of the contrast agent for comparison of pre and post images. This long interval between injection and imaging is needed in order to allow for sufficient time for macrophage phagocytosis to occur. Patients will be placed supine in a 3T MR scanner, the area of the transplant kidney will be covered by a dedicated surface coil, and T1- and T2-weighted MR images will be obtained of the transplant, using axial and/or coronal T1-LAVA and T2-FSE sequences as well as multi-TE SE, multi-TI IR sequences and QSM sequences for iron quantifications. All MR images will be transferred to a postprocessing workstation and T1- and T2-relaxation times will be calculated of the kidney transplant as well as adjacent muscle and bone marrow in a pelvic bone as an internal standard. The patients will undergo a routine biopsy of their transplant within 3 weeks before or (preferably) after the MRI study. Based on renal biopsies and histopathology results, patients will be divided into groups of "no rejection" and "positive rejection". Various MRI and histopathological parameters will be compared between these two groups using student's t-tests, an analysis of variance (e.g. for comparison of data from multiple time points, multiple pulse sequences, different histopathologic stains) and regression analyses. Significant differences will be assigned for a p-value of less than 0.05.

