Endpoint: To generate a non-invasive, easily applicable and widely available MR imaging test for evaluation of kidney transplant rejection. Primary endpoint is to develop a sensitive and reliable, non-invasive and quantitative imaging test for detection of macrophages in kidney transplants as a biomarker for rejection. As a secondary endpoint, since different oxygenation states of iron have scaled but measurable changes on the inherent tissue magnetic susceptibility, we plan to also evaluate the utility of simultaneously generated 3D maps of arterial and venous supplies of kidney transplants, provided by our imaging method, in comparison with ultrasound as the current diagnostic standard. The ultimate goal is to provide a comprehensive evaluation of the morphology, vascular supply and host immune responses in kidney transplants with one single, non-invasive and comprehensive diagnostic test.

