8. PARTICIPANT POPULATION

a. Planned Enrollment

30 solid organ transplant recipients, to monitor for transplant rejection and evaluate the utility of 3D maps of arterial and venous supplies to the transplant.

b. Age, Gender, and Ethnic Background

We expect all 30 participants to be pediatric kidney transplant patients, any gender, any ethnic background. Referrals only accepted from Drs. [name] and [name].

c. Vulnerable Populations

We expect all 30 participants to be pediatric kidney transplant patients. The study adds on a non-invasive imaging study to the standard of care for these patients. Informed Consent and Assent practices will be followed.

d. Rationale for Exclusion of Certain Populations

NA

e. Stanford Populations

NA

f. Healthy Volunteers

NA

g. Recruitment Details

Participants will be referred from their treating physician's office, either [name] or [name] invitation only .

h. Eligibility Criteria

i. Inclusion Criteria

recipient of a solid organ transplant, scheduled for a standard of care rejection survey

ii. Exclusion Criteria

contraindication for MRI hemosiderosis/hemochromatosis, diagnosed based on routine lab values obtained within 30 days prior to MRI scan and/or precontrast MRI

i. **Screening Procedures**

Referring treating physician discusses study with potential participant. Potential participant is referred to study coordinator to schedule a screening visit. The protocol director or other IRB approved trained personnel complete consent/assent, MRI screen, and chart review lab values .

j. **Participation in Multiple Protocols**

We will ask the participant and their family if they are enrolled in any other studies. If they are enrolled in a drug study, we will consult with the other PI before proceeding to avoid any conflicts.

k. **Payments to Participants**

Reimbursement for gas/mileage to a max of \$50 per visit to the family/driver. A \$20 Amazon gift card to the participant.

l. **Costs to Participants**

No research costs will be charged to the participants.

m. **Planned Duration of the Study**

The study is expected to enroll patients for two years, with data analysis continuing for possibly another year total: three years . i screening: 20-45 minutes; ii 90-120 minutes; iii 3-5 hours per participant, including 3D reconstructions, plus another 40-100 hours of collective data analysis.

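### Does the CD163 macrophage score leave some biopsies without a grade, so that the T2* regression needs a rewritten score?

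*SAP*

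**What the plan says.** The SAP, under Histopathology, opens the scoring rule with the zero grade and says the reading was blinded: "The CD163 stained slides were scored blinded as follows: no stained cells = 0". The next two grades are "G10 positive cells/hpf present in G25 % of biopsy = 1, 910 positive cells/hpf in 26–50 % of biopsy = 2", and the top grade is "positive cells in 950 % of biopsy = 3". With the damaged signs restored, grade 1 is fewer than 10 cells per high-power field in under 25% of the biopsy, grade 2 is more than 10 in 26–50%, and grade 3 is more than 10 in over 50%. There is no default grade and no statement of which dimension prevails when density and extent disagree.

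The score has one use, given under Data Analysis: "T2* relaxation times were correlated with the CD163 score, using a linear regression analysis". The Protocol adds no scoring rule. Section 2a refers only in general terms to "different histopathologic stains) and regression analyses". Section 2g sets the primary endpoint as a "quantitative imaging test for detection of macrophages in kidney transplants as a biomarker for rejection".

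**The concern.** A grading scale should give every possible specimen exactly one grade. This one appears not to. A biopsy with a small dense focus is too dense for grade 1 and too limited in extent for grade 2. A biopsy with sparse cells throughout is too extensive for grade 1 and too sparse for grades 2 and 3.

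The point seems to matter because the endpoint names macrophages, and this regression is the only specified analysis that sets T2* against a tissue measure of them. If the rule is applied to the letter, an in-between biopsy drops out, which costs precision and could bias the result if the loss is related to T2*. If it is graded anyway, the grade rests on a convention that nobody wrote down.

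**Working it through.** **Is the gap produced by the damaged signs?** No. The sign before 50% in grade 3 must be a greater-than sign, strict or inclusive, which fixes the 9. Reading G as greater-than would make grade 1 run into the 26–50% band and break the ordering, so G is a less-than sign, strict or inclusive. Under all four combinations of strict and inclusive signs, dense staining at or below 25% and sparse staining at 26% or more stay ungraded. (Under strict signs, exactly 25% and exactly 10 cells are ungraded too. These are boundary trifles and are ignored below.)

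**Which combinations lack a grade, and how far apart are reasonable completions?** Two rules agree with every grade the SAP states. One lets extent decide. The other lets density decide: sparse is never above 1, dense is never below 2, and extent separates 2 from 3.

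| Density, extent | Stated | Extent decides | Density decides | Difference |
|---|---|---|---|---|
| sparse, up to 25% | 1 | 1 | 1 | 0 |
| sparse, 26–50% | none | 2 | 1 | 1 |
| sparse, over 50% | none | 3 | 1 | 2 |
| dense, up to 25% | none | 1 | 2 | 1 |
| dense, 26–50% | 2 | 2 | 2 | 0 |
| dense, over 50% | 3 | 3 | 3 | 0 |

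Three of six combinations are ungraded. A choice of rule moves such a biopsy by one grade in two of them and by two grades in the third.

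**What would dropping biopsies cost?** This is hypothetical, since the SAP does not say that any were dropped. On the Fisher-z scale the standard error of a correlation is 1/√(n − 3), so losing k of n biopsies widens the interval by √((n − 3)/(n − k − 3)). This is approximate for a four-level score. The Protocol, section 8a, plans "30 solid organ transplant recipients, to monitor for transplant rejection". The number of scored biopsies is not given, so n = 20 and n = 30 are assumptions, as is k.

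- n = 30: √(27/26) = 1.019 for k = 1; √(27/24) = 1.061 for k = 3; √(27/21) = 1.134 for k = 6.
- n = 20: √(17/16) = 1.031 for k = 1; √(17/14) = 1.102 for k = 3; √(17/11) = 1.243 for k = 6.

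One lost biopsy therefore costs 2–3% in width. Reaching about 10% takes 3 of 20, or 5 of 30 (√(27/22) = 1.108). Nothing in the documents supports a k of that size, and k = 0 is possible.

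**Which analyses depend on the score?** The t tests compare rejecting with non-rejecting allografts, and the ANOVA adds native kidneys. Rejection is judged on the Banff 2013 criteria, not on CD163. Only the regression is exposed.

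**What does the SAP suggest happened?** It is written in the past tense: the slides were scored, blinded, and the computations were done. No slide is described as unscorable. Dropout is therefore the less natural reading, and grading by judgement the more natural one. If the blinding covered the MRI, such judgement cannot follow T2*. It adds noise to the score, which tends to weaken an association rather than create one.

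**The case for a change.** The best case for a change is that nearest grade is not defined here. Dense staining in 10% of a core differs from grade 1 in one dimension and from grade 2 in one dimension, so two careful readers could disagree, and blinding guards against bias without making the score reproducible. The ungraded patterns are also plausible. The Protocol's background says that macrophages gather where tissue is damaged and that biopsies are subject to sampling error, which fits a small dense focus. The remedy would be cheap: a sentence, a count and a sensitivity analysis.

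Part of this stands. The rule is incomplete as written, no other section completes it, and a report of the regression would be clearer if it said how in-between slides were graded and how many there were.

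The rest does not carry a change to the plan. Plausibility is not frequency. The extent bands already rise in step with grades 1 to 3, so a pathologist has an obvious, though unwritten, default. Asking someone to state which dimension decides does not identify a better rule, and the documents give no ground for choosing one. With scoring and computation already reported as done, the wording would be post hoc and could not restore prespecification.

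**Conclusion.** The concern is right about the wording and does not show harm. Three of six density-by-extent combinations have no written grade, and the choice of convention could shift an affected biopsy by one or two grades on a four-level scale. That affects one regression and leaves the rejection comparisons untouched.

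This is a missing detail that a blinded pathologist fills sensibly in the course of reading, so no change to the plan follows. The conclusion assumes that every stained slide received a grade, which the SAP implies but does not state, and that the blinding covered the MRI, which the SAP does not spell out. The interval-widening figures are illustrations for an assumed number of lost biopsies, not evidence of any loss. At most this is a minor point of clarity for the report of results.

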1. PURPOSE OF THE STUDY

a. Brief Summary

The purpose of this study is to develop a non-invasive imaging test for in vivo detection of kidney transplant rejection. We propose to use an FDA-approved iron supplement "off label" as a marker for macrophages. After intravenous injection, the iron compound is taken up by macrophages and causes a detectable signal on magnetic resonance (MR) images. Since kidney transplants that undergo a rejection contain macrophages, but not unimpaired transplants, this approach should enable us to detect kidney transplant rejection with a simple imaging test.

b. Objectives

If successful, this ferumoxytol-based MR imaging test could reduce the number of renal allograft biopsies and associated anesthesia. If at least some of these biopsies could be replaced by a non-invasive imaging test, this would have immense impact on patient management and patient quality of life, and reduce health care costs. Exclusion of renal allograft rejection based on ferumoxytol-enhanced MRI would help avoid unnecessary biopsies, accelerate diagnostic workup of other reasons for an impaired renal function, and ultimately, improve patient outcomes. The proposed non-invasive imaging test could be in principle also applied to evaluation of other solid organ or stem cell transplants. Data derived from this project will be used as preliminary data for a subsequent NIH grant application.

c. Rationale for Research in Humans

Initial studies have been performed in animal models. We now have to verify the animal model results can be reproduced in patients.

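### No planned analysis estimates diagnostic accuracy, although the primary endpoint is a sensitive MRI test for macrophages as a biomarker for rejection

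*SAP*

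**What the plan says.** Protocol 2g (Study Endpoint(s)) gives the primary endpoint as to "develop a sensitive and reliable, non-invasive and quantitative imaging test for detection of macrophages in kidney transplants as a biomarker for rejection"; 9d (Study Conclusion) repeats it. Protocol 1b (Objectives) describes the hoped-for use: "Exclusion of renal allograft rejection based on ferumoxytol-enhanced MRI would help avoid unnecessary biopsies". The same section says: "Data derived from this project will be used as preliminary data for a subsequent NIH grant application".

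The reference standard is biopsy. Protocol 2a (Procedures) uses it to sort patients into rejection and no-rejection groups, and the SAP's Histopathology section applies the Banff 2013 criteria and a blinded 0–3 CD163 score.

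On analysis, protocol 2a says: "Various MRI and histopathological parameters will be compared between these two groups using student's t-tests", together with analysis of variance and regression analyses that it does not specify further. The SAP's Data Analysis section has three items:

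- a t test: "GFR and MRI data were compared between patients with non-rejecting and rejecting allografts using the two-sided t test"
- an ANOVA of mean T2* (whole kidney, cortex, medulla) over native, non-rejecting and rejecting groups
- a regression: "T2* relaxation times were correlated with the CD163 score, using a linear regression analysis"

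All use an alpha of 0.05. Neither document names an AUC, an estimate of sensitivity or specificity, a cut-off, or a confidence interval for any of these.

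**The concern.** Sensitivity describes how individual patients are classified. A test of a difference in means asks whether two groups differ on average. A small p-value shows that MRI carries some information about rejection, but not how many rejections it would miss or how many sound grafts it would flag.

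A group comparison is a reasonable first step for a pilot, and finding no difference would count against the test. A significant difference, however, leaves the word *sensitive* in the primary endpoint without an estimate. It also gives the planned grant application no accuracy figure from which to design the next study. The study already pairs MRI with biopsy, so the data for such an estimate will exist.

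**Working it through.** The documents give no power calculation, effect size, SD, expected rejection rate or accuracy target, so there is no figure of the plan's own to reproduce. The check has three steps.

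**1. What each planned analysis returns.** The t test and ANOVA return differences in means and p-values. The T2*–CD163 regression returns a slope or correlation, which bears on the macrophage part of the endpoint but is an association, not accuracy. The protocol's unspecified regressions could in principle include a logistic model, but no accuracy output is named and the SAP specifies only linear regression.

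**2. What a significant t test implies for classification.**

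- From the documents: planned enrollment of 30 (protocol 8a), two-sided t test and alpha 0.05 (SAP, Data Analysis).
- Assumed: normal data, equal SDs, 20–50% rejecting. N = 20 is shown as well, because the SAP has a native-kidney group and the documents do not say whether those patients count among the 30.
- Standardised difference that just gives a two-sided p: d = t(1 − p/2, N − 2) × √(1/n₁ + 1/n₂).
- AUC = Φ(d/√2).
- Specificity at 90% sensitivity = Φ(d − 1.2816).

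Example, 6 rejecting and 24 not, p = 0.05: d = 2.048 × √(1/6 + 1/24) = 2.048 × 0.4564 = 0.935. AUC = Φ(0.661) = 0.746. Specificity = Φ(−0.347) = 0.364.

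| N | p | Split (rejecting/not) | d | AUC | Specificity at 90% sensitivity |
|---|---|---|---|---|---|
| 30 | 0.05 | 6/24 | 0.935 | 0.746 | 0.364 |
| 30 | 0.05 | 9/21 | 0.816 | 0.718 | 0.321 |
| 30 | 0.05 | 12/18 | 0.763 | 0.705 | 0.302 |
| 30 | 0.05 | 15/15 | 0.748 | 0.702 | 0.297 |
| 30 | 0.01 | 6/24 | 1.261 | 0.814 | 0.492 |
| 30 | 0.01 | 15/15 | 1.009 | 0.762 | 0.393 |
| 30 | 0.001 | 6/24 | 1.677 | 0.882 | 0.654 |
| 30 | 0.001 | 15/15 | 1.342 | 0.829 | 0.524 |
| 20 | 0.05 | 4/16 | 1.174 | 0.797 | 0.457 |
| 20 | 0.05 | 6/14 | 1.025 | 0.766 | 0.399 |
| 20 | 0.05 | 8/12 | 0.959 | 0.751 | 0.373 |
| 20 | 0.05 | 10/10 | 0.940 | 0.747 | 0.366 |

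The p = 0.05 rows are the boundary case. Each row treats the observed difference as the true one, so it illustrates what a given p-value can mean and does not forecast the result.

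**3. What the added analysis could deliver.** If all n rejections are detected, the exact two-sided 95% lower limit for sensitivity is 0.025^(1/n):

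| n rejections | 4 | 6 | 9 | 10 | 12 | 15 |
|---|---|---|---|---|---|---|
| Lower limit | 0.398 | 0.541 | 0.664 | 0.692 | 0.735 | 0.782 |

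For the AUC, the Hanley–McNeil variance is [A(1 − A) + (n₁ − 1)(Q₁ − A²) + (n₂ − 1)(Q₂ − A²)]/(n₁n₂), with Q₁ = A/(2 − A) and Q₂ = 2A²/(1 + A). At A = 0.80 and N = 30, the 95% half-width is 0.227 for 6/24 and 0.162 for 15/15.

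**The case against.** The strongest reply is that the endpoint speaks of detecting macrophages, and the T2*–CD163 regression addresses that directly. This is partly right, and the regression should stay. But the endpoint ties macrophages to rejection, and a slope does not measure sensitivity for either.

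A second reply is that this is an early study. The objectives are conditional, the data are described as preliminary, every patient has a biopsy anyway, and the Benefits section places "validating a method for accurately assessing rejection status/health of an allograft" in the long term. That stands: no clinical decision in this study rests on an accuracy figure, and the planned tests are not invalid. It does not remove the gap, since preliminary data for a diagnostic test are more useful with an accuracy estimate and its uncertainty.

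Third, the numbers are small, the SAP is written in the past tense, and the illustration rests on assumptions. All true. The accuracy analysis can only be descriptive, and choosing a measurement now cannot be shown to be independent of the results.

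Two caveats carry over to any accuracy estimate. Biopsy may fall up to three weeks before or after MRI (protocol 2a), so the reference status may differ from that at imaging. And protocol 2a names T1 and T2 relaxation times, whereas the SAP analyses T2*.

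**Conclusion.** The concern holds. Followed exactly as written, the plan can report whether MRI values differ between rejecting and non-rejecting allografts and whether T2* tracks CD163, but not how sensitive or specific the test is. That finding rests on the text alone.

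Its size is illustrative and depends on the assumed split, normality and equal SDs. With 30 allografts, a result between p = 0.05 and p = 0.001 is compatible with an AUC anywhere from 0.70 to 0.88, and with specificity at 90% sensitivity from 30% to 65%. With 20 allografts, p = 0.05 corresponds to an AUC of 0.75–0.80 and specificity of 37–46%.

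Even perfect detection would leave a lower 95% limit for sensitivity of 54–78% (6–15 rejections among 30) or 40–69% (4–10 among 20). The study can therefore supply an accuracy estimate but cannot establish that MRI rules out rejection. This should be fixed, though it does not invalidate the planned comparisons.

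**What to change.** Add one paragraph to the SAP's Data Analysis section:

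- **Accuracy measure:** the AUC with 95% CI of one named measurement for Banff-defined rejection on biopsy. Whole-kidney mean T2* is a natural choice because the SAP already analyses it.
- **Population:** biopsied allografts only; leave native kidneys out.
- **Cut-offs:** sensitivity and specificity with 95% CIs. Use exact intervals for a cut-off fixed in advance, and optimism-corrected estimates (bootstrap or leave-one-out) for one derived from the data.
- **Existing analyses:** keep the t test, ANOVA and CD163 regression, naming the last as the analysis of the macrophage part of the endpoint.
- **Labelling:** call the accuracy analysis exploratory and specified late, and report the interval between MRI and biopsy beside it.
- **Claims:** base any statement about excluding rejection on the lower confidence limit for sensitivity.

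The cost is the paragraph and a few hours of analysis on data already paired, with no added patients or procedures. The downsides are post hoc status, wide intervals, and some work outside Excel: a rank-based AUC and exact limits can be done in a spreadsheet, but a bootstrap correction is better run in a statistical package.
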